Observation Plan
Drug Substance Anastrozole
Code NIS-ODE-ARI-2008/1
Date 19 Mar 2009 (Version 1.4)

Observation Plan

Drug Substance Anastrozole

Code NIS-ODE-ARI-2008/1

19 Mar 2009 (Version 1.4)

Arimidex: Compliance and arthralgias in clinical therapy (COMPACT):
An in practice assessment of arthralgias and related costs as well as compliance in the first year of anastrozole therapy

Sponsor:

AstraZeneca GmbH
[name]
[name] / Germany
[contact]

Responsible Medical Officer:

Responsible Statistician:

Planned non-interventional study period:

Q1 2009 – Q4 2010

SYNOPSIS

Arimidex: Compliance and arthralgias in clinical therapy (COMPACT):
An in practice assessment of arthralgias and related costs as well as compliance in the first year of anastrozole therapy

Centre(s) and number of patients planned

Approximately 700 centres in Germany will participate in this in practice evaluation program, including specialised clinics and office based gynaecologists or oncologists.

It is planned to enroll 3212 patients in this NIS.

Program period

Estimated date of first patient enrolled	Q1 2009
Estimated date of last patient enrolled	Q1 2010
Estimated date of last patient completed / NIS end	Q4 2010
Estimated date of analysis of three months data	Q2 2010
Estimated date of final analysis	Q4 2010
Estimated date of finalisation of report	Q2 2011

EXTERNAL ADVISING COMMITTEES

Steering Committee

-

Objectives:

Primary objective:

Assessment of arthralgia scores and patients` compliance within the first year of anastrozole treatment¹, stratified by upfront and switch therapy as well as assessment of the relationship between compliance and arthralgia scores.

Secondary objectives

Incidence of arthralgias and arthralgia characteristics within the first year of anastrozole therapy¹ stratified by upfront and switch therapy and assessment of the relationship of arthralgia incidence and arthralgia characteristics to patients` compliance.

Retrospective assessment of incidence of pre-existing arthralgias before start of anastrozole treatment, stratified by upfront and switch therapy.

Descriptive assessment of arthralgia therapy and of costs of arthralgia therapy, stratified by upfront and switch therapy.

The assessment of compliance and of arthralgia therapy will be compared to and validated by the corresponding data obtained by the sick funds of the patients.²

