5. CENTRE SELECTION AND PLANNED NUMBER OF CENTRES

This NIS study is a non-interventional, multi-centre, observational study with approximately 700 specialised clinics and office based gynaecologists or oncologists. Study Centres will be selected in concern of the criteria of the medical experiences and the knowledge of the disease of study investigators.

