6. PATIENT SELECTION AND PLANNED NUMBER OF PATIENTS

Patients are eligible for inclusion in this NIS if they have taken anastrozole either upfront or following two to three years of tamoxifen treatment (“switch”) for at least three and not more than six months prior to offering an individual participation in this program. Treatment should follow local therapy guidelines and standard practice. Treatment decisions for patients participating in this study including assessments or supportive therapy during follow-up visits will also follow guidelines and remain independent of the program.

The patient population will include postmenopausal women with hormone-receptor positive primary breast cancer scheduled for adjuvant upfront endocrine treatment with anastrozole or following two to three years of tamoxifen treatment (“switch”) according to the current SmPC (Appendix C). Patients will have taken anastrozole for at least three months and not more than six months before the start of the study.

It is planned to enrol and document 3212 patients in this NIS. Further details regarding the objectives and the sample size consideration can be found in Section 3 and 11.5..

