11.1 Statistical evaluation – general aspects

A comprehensive Statistical Analysis Plan (SAP) covering details of all methods used to analyze the various parameters will be prepared before database lock of the 3 months data. The SAP will be reviewed, and if needed, updated before this first data base lock.

The disposition of patients with regard to

- the number of patients enrolled,
- the number of patients treated with anastrozole (upfront and following two to three years of tamoxifen treatment),
- the number of patients who discontinued prematurely from the anastrozole therapy within the study period,
- the number of patients who discontinued prematurely from this NIS within the present observational period,
- the number of patients who completed the NIS up to 3, 6, and 9 months after study start,
- the number of patients who are still taking anastrozole up to the time point of the present statistical analysis of this NIS

will be displayed by specialized clinic (including overall). The disposition of the patients in the subsequent final analysis will be displayed in the same way.

Patients without any documented start of an endocrine therapy (e.g. missing information on prescriptions) will be excluded from all statistical analyses, but will be displayed in all data listings.

All treated patients who discontinued prematurely from the anastrozole therapy and/or the NIS (according to the corresponding CRFs) will be listed by clinic; at least the time-point of discontinuation, the main reason for discontinuation and relevant data of exposure to anastrozole will be presented.

The following text refers to more general statistical key-principles based on the statistical analysis data sets, i.e. the intent-to-treat population and the safety population:

Binary, categorical and ordinal parameters will be summarized by means of absolute and percentage numbers (including ‘missing data’ as valid category at Visit 1). Numerical data will be summarized by means of standard statistics (i.e. number of available data, mean, standard deviation, minimum, median, maximum, lower and upper quartile). Wherever useful, the summary statistics will be presented by specialized clinic (including overall) and/or visit.

In addition, adequate figures (e.g. bar charts, Box-Whisker-Plots) may be presented to summarize the results for some parameters also in a graphical way.

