All statistical tests will be performed two-sided at a 5% level of significance. However, the p-values of all statistical tests will be interpreted only in a descriptive-exploratory way. Two-sided confidence intervals will be displayed for important variables. Appropriate methods will be used to derive confidence intervals, depending on data nature and distribution. All safety and tolerability data (excluding data obtained on arthralgias) will be presented in a purely descriptive manner. Data from patients, who stopped anastrozole treatment and continued adjuvant endocrine treatment with a different medication will be presented in descriptive way only.

All statistical analyses will be performed using the SAS[®] system.

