11.2 Description of outcome variables

The co-primary objective of this NIS will be the evaluation of arthralgia scores and patients’ compliance. Secondary, arthralgia management and related costs (health economic evaluation) as well as the perception of side-effects will be evaluated. Data concerning arthralgia management will be compared to and validated by data obtained by the GWQ.

Compliance:

Compliance is defined by the percentage number of patients being ‘compliant’ to anastrozole therapy, based on the following information collected by the doctor at 0, 3, 6 and 9 months after study start:

1) Question about the daily intake of anastrozole (to be answered by the investigator):

”The patient was instructed to take 1 anastrozole tablet per day. However, it’s still possible that the intake has sometimes been forgotten. How many tablets, according to your impression of the patient, has the patient actually taken during the last year?”

Scoring:	0 – none	0%
	1 – few	[0% ; 20%]
	2 – less than half	[20% ; 40%]
	3 – approximately half	[40% ; 60%]
	4 – more than half	[60% ; 80%]

5 – almost all	[80% ; 100%]
6 – all	100%.

- 2) Question about the daily intake of anastrozole (to be answered by the patient in the patient questionnaire)
”You were instructed to take 1 anastrozole tablet per day. However, it’s still possible that the intake has sometimes been forgotten. How many tablets have you actually taken during the last year?”

Scoring: 0 – none	0%
1 – few	[0% ; 20%]
2 – less than half	[20% ; 40%]
3 – approximately half	[40% ; 60%]
4 – more than half	[60% ; 80%]
5 – almost all	[80% ; 100%]
6 – all	100%.

- 3) A patient will only be defined as being ‘compliant’ when the answer of the doctor **and** the patient score ‘5’ or ‘6’ concerning the question regarding the number of tablets actually taken.

Arthralgias

Arthralgias will be characterized by VAS scores containing 14 items.

Arthralgias will be summarized by incidence, localization, onset, duration, intensity, and relationship to study drug, diagnostics and arthralgia management (e.g. medication, physiotherapy, doctor’s visits, change of life style etc.). Arthralgia characteristics will be particularly assessed using VAS scores (Appendices E and F).

Perception of side-effects

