11.4.1 Outcome variables

The objectives outlined in chapter 3 will be analysed as follows:

Primary objective:

Assessment of arthralgia scores and patients' compliance within the first year of anastrozole treatment¹, stratified by upfront and switch therapy as well as assessment of the relationship between compliance and arthralgia scores.

The absolute number and percentage of compliant patients will be calculated. Groups will be compared with Fisher's exact test

From the arthralgia scores an overall score will be calculated (sum of 14 single item scores divided by 14). Groups will be compared using t-test.

Relationship between compliance and arthralgia scores will be assessed using logistic regression analysis.

Of primary interest are the 3 months data (data obtained within the first three months of anastrozole therapy). Secondly, the other time points will be evaluated.

Secondary objectives:

Incidence of arthralgias and arthralgia characteristics within the first year of anastrozole therapy¹ stratified by upfront and switch therapy and assessment of the relationship of arthralgia incidence and arthralgia characteristics to patients' compliance.

The absolute number and percentage of patients with at least one event of arthralgia within pre-defined intervals (0-3, 3-6, 6-9, 9-12 and 12+ months after the start of anastrozole treatment) will be calculated.

Characteristics of arthralgias within each time interval will be evaluated descriptively stratified by upfront and switch therapy:

- Maximum intensity, localization, relationship to study drug, diagnostics and arthralgia management presenting number and percentage of each category.
- Time between start of anastrozole therapy and first incidence of arthralgia will be analysed using the Kaplan-Meier method.

Maximum duration of arthralgias will be evaluated descriptively, presenting standard statistics.

Retrospective assessment of incidence of pre-existing arthralgias before start of anastrozole treatment, stratified by upfront and switch therapy.

The absolute and percentage number of patients with pre-existing arthralgias will be calculated stratified by upfront and switch therapy.

Descriptive assessment of arthralgia therapy and of costs of arthralgia therapy, stratified by upfront and switch therapy.

Evaluation will be performed descriptively with standard statistics and associated with cost modules of sick funds.

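### The primary compliance analyses take no account of centre, although about 700 centres contribute some 4.6 women each and compliance depends partly on the doctor's impression; a centre-robust variance is a cheap improvement

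*Protocol*

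**What the plan says.** Section 5 plans "approximately 700 specialised clinics and office based gynaecologists or oncologists", and Section 6 states: "It is planned to enrol and document 3212 patients in this NIS".

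Section 11.2 builds compliance from two answers. The investigator estimates the tablets taken "according to your impression of the patient", and the patient answers the same question in her questionnaire. Both must score 5 or 6.

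Section 11.4.1 fixes the primary analyses: Fisher's exact test for compliance, a t-test for the mean of the 14 VAS items ("Groups will be compared using t-test"), and logistic regression for the relation between the two. No centre term, stratum or cluster-adjusted variance is mentioned. Section 11.5 sizes the study from independent patients with no design effect.

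Centre appears in Section 11.1 only as a level for displays and listings: "Wherever useful, the summary statistics will be presented by specialized clinic (including overall) and/or visit". The same section says "All statistical tests will be performed two-sided at a 5% level of significance", but adds that "the p-values of all statistical tests will be interpreted only in a descriptive-exploratory way". It leaves the confidence-interval method open, to suit the data.

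**The concern.** Women documented by the same practice are unlikely to be statistically independent on compliance. A doctor who tends to score 4 where a colleague would score 5 shifts the result of every woman that doctor rates. Requiring the patient's answer as well dilutes this but does not remove it. Fisher's exact test assumes independent women and has no place for centre. Logistic regression without a centre effect or robust variance makes the same assumption.

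Two results could suffer. The first is the overall compliance percentage, a headline result: if its interval is computed from independent binomial counts, it is too narrow whenever the intra-centre correlation is positive. The second is the upfront-versus-switch comparison, but only to the extent that therapy type also clusters by centre.

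Displays by clinic do not help. With three to five women per clinic they say little about any one clinic and leave the standard errors of the pooled analysis unchanged.

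**Working it through.** **The plan's own figures.** For 0.44 against 0.50, two-sided 5%, 80% power, mean proportion 0.47:

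n = [1.960 × √(2 × 0.47 × 0.53) + 0.842 × √(0.44 × 0.56 + 0.50 × 0.50)]² / 0.06² = 1085.02, so 1086.

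With the continuity correction, n × ¼ × (1 + √(1 + 4/(1085.02 × 0.06)))² = 1118.1, so 1119 per group, as in Section 11.5. The t-based calculation for a difference of 0.4 with SD 2 gives 393.4, so 394, also as stated. Neither contains a design effect. After 30% loss, 3212 × 0.70 = 2248 women remain against 2 × 1119 = 2238 needed, a margin of 10.

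**Women per centre.** 3212/700 = 4.59 enrolled; 2248/700 = 3.21 evaluable.

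**Assumptions.** The protocol gives no intra-centre correlation (ICC), no spread of centre sizes and no upfront/switch mix by centre. I take ICC 0.05, 0.10 and 0.20, and a coefficient of variation (CV) of centre size of 0 or 1.

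**Design effect for an overall percentage.** DE = 1 + (m(1 + CV²) − 1) × ICC, with m = 3.21. The true standard error is √DE times the unadjusted one, so the unadjusted one is too small by 1 − 1/√DE.

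| CV | ICC | DE | √DE | Unadjusted SE too small by |
|---|---|---|---|---|
| 0 | 0.05 | 1.11 | 1.05 | 5% |
| 0 | 0.10 | 1.22 | 1.11 | 10% |
| 0 | 0.20 | 1.44 | 1.20 | 17% |
| 1 | 0.05 | 1.27 | 1.13 | 11% |
| 1 | 0.10 | 1.54 | 1.24 | 20% |
| 1 | 0.20 | 2.08 | 1.44 | 31% |

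Near 50% compliance the unadjusted half-width is 1.96 × √(0.25/2248) = 2.07 percentage points. Multiplied by 1.05 to 1.44 it becomes about 2.2 to 3.0 points.

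**Simulation.** 700 centres, 2248 women, normal outcome, 4000 repetitions per case, unadjusted analysis at nominal 5%. Centre sizes were drawn at random around their expected values. This adds about 1/m to CV², so the design effect becomes about 1 + m × ICC (1.16, 1.32, 1.64) for equal expected sizes and 1 + 2m × ICC (1.32, 1.64, 2.28) for very uneven ones.

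| Result at ICC 0.05 / 0.10 / 0.20 | Equal expected sizes | Very uneven sizes |
|---|---|---|
| Coverage of 95% interval, overall mean | 93 / 91 / 87% | 91 / 87 / 81% |
| Type I error, strategies mix freely within centres | 4.7 / 5.1 / 5.1% | 5.3 / 5.5 / 4.4% |
| Type I error, mix varies widely by centre | 5.5 / 6.5 / 7.3% | 5.8 / 8.1 / 9.8% |
| Type I error, each centre uses one strategy | 6.4 / 9.4 / 12.7% | 7.8 / 12.2 / 20.2% |

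The formula agrees on coverage: 2Φ(1.96/√1.16) − 1 = 93% and 2Φ(1.96/√2.28) − 1 = 81%. The loss of coverage does not depend on how therapy is distributed over centres. The excess type I error depends almost wholly on it.

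**The case against.** The strongest reply is that the protocol claims little that could be wrong. Section 11.1 makes all p-values exploratory and leaves the interval method open, and Section 11.4 defers detail to the SAP. Covariates in the regression and the variance behind an interval are ordinary SAP content. Most of this stands. What remains is that Section 11.4.1 itself names Fisher's exact test and the t-test, which cannot carry centre, and that nothing in the document asks for centre to be considered in any estimate.

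Several stronger readings are tempting but unsupported:

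- *The plan's intervals are wrong.* The document does not say that they assume independence; no method is fixed.
- *One doctor rates all of a centre's women.* Section 8.1 allows the investigator or a delegate to enter data, and sites include specialised clinics. A single rater is plausible in an office practice but is not stated.
- *Lenient doctors distort the t-test.* The VAS score comes from the patient's own paper questionnaire (Section 8.2), so that route reaches compliance only. Likewise, a doctor's assessment could enter both sides of a regression only in the secondary analyses that use doctor-recorded arthralgia.
- *Upfront or switch is a property of the site.* Switch status is a woman's treatment history of two to three years of tamoxifen. How far it clusters by centre is unknown.
- *The real error rate is 17% to 20%.* That needs ICC 0.20, very uneven centres and one strategy per centre all at once.
- *Section 11.1 promises 700 clinic tables.* It offers clinic summaries only where useful.

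**Conclusion.** The point holds as a modest improvement for compliance, not as a breached error rate. Section 11.4.1 fixes patient-level analyses without centre, while part of the compliance endpoint is a doctor's impression gathered at about 700 sites.

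The effect is clearest for the overall and stratum compliance percentages. If their intervals are computed without adjustment, an assumed ICC of 0.05 to 0.20 lowers overall coverage from 95% to somewhere between 93% and 81%, depending on the ICC and on how uneven the centres are. For upfront against switch, the unadjusted test is sound if strategies mix within centres and moderately liberal if the mix varies widely. It is seriously liberal only if therapy type follows the centre.

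All these sizes rest on assumed ICCs, because the document gives none. They come from a normal-outcome simulation, so they are approximate for a percentage. If the ICC is negligible, results will hardly change.

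**What to change.** In Section 11.4.1, or in the SAP with a pointer from there:

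1. Analyse compliance, and its regression on the arthralgia score, with GEE or cluster-robust standard errors by centre, or with a random centre intercept. Fisher's exact test may stay as a supporting result.
2. Use centre-robust 95% intervals for the overall and stratum compliance percentages.
3. Apply the same variance to the VAS score comparison for consistency.
4. Report the intra-centre correlation, so that readers can see whether it mattered.

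The cost is a few sentences and standard procedures in SAS, which the plan already uses. The centre number is already recorded (Section 8.2.1), so no new data are needed. The downside is slightly wider intervals.

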In this Non-Intervention Study (NIS) all participating patients will receive standard routine care for breast cancer and information material with general background information on breast cancer, endocrine treatment, coping with the diagnose and lifestyle in order to enhance compliance [22]. This NIS aims to assess incidence and characteristics of arthralgias as a therapy-limiting and compliance-limiting side-effect, and assesses whether the incidence and severity of arthralgias is different in upfront anastrozole therapy and in anastrozole therapy following two to three years of tamoxifen treatment. Furthermore, compliance will be assessed and compared in patients experiencing arthralgias and patients not experiencing arthralgias. Arthralgia incidence and characteristics will be correlated to patient's compliance, and factors influencing arthralgias and compliance will be identified. Arthralgia characteristics will be particularly assessed using a validated VAS scale (Appendices E and F). Subjective perception of side-effects will be evaluated by psycho-oncologic scales (Appendices E and F). Costs of arthralgia therapy, as well as all costs of breast cancer therapy will be assessed and described in a descriptive manner. This study is part of a cooperation project with the GWQ (an organization including currently 19 sick funds). For patients who are insured in one of these sick funds and who consented to transfer of pre-defined data, study data will be compared to and validated by sick fund data.

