8.1.2 Documentation at baseline

The following data should be documented at baseline:

Demographics	Height (cm) Weight (kg) BMI
Menopausal status	
Age of patient when entering menopause	
Did the patients receive any hormone replacement therapy before?	Yes, no; if yes => duration of hormone replacement therapy?
Specification of hormone replacement therapy	Estrogen only (dose of estrogen); Estrogen-gestagen combination (dose of estrogen)
Concomitant diseases	Answers for each listed point (no, yes – please specify, unknown) Cardio-circulatory system

	
vascularly system skeleton, musculature (i.e. rheumatoid arthritis, arthralgias, osteoarthritis, back pain, capral tunnel syndrome; soft tissue rheumatism; other musculature and joint discomfort) if arthralgias occurred => pre-existing arthralgias before anastrozole therapy? => if yes: intensity? localisation? duration?; => any arthralgia occurrence after the start of anastrozole therapy? if yes => Arthralgia AE module
 
Urogenital system Central nervous system Gastrointestinal system Metabolic diseases Hot flushes Headache / migraine Other

Primary diagnosis of breast cancer	Date of primary diagnosis
Number of tablets currently taken by patient per day	
Localisation of primary tumour	
Anastrozole indication	Upfront or following tamoxifen treatment if following tamoxifen treatment: duration of tamoxifen therapy
Breast cancer therapies	Performance of post-operative radiation therapy (no, yes) Performance of neo-adjuvant chemotherapy (CHT) (no, yes; number of cycles) Performance post-operative chemotherapy (no, yes; number of cycles)
Treatment compliance: doctor`s assessment	Estimation of compliance by doctor`s judgement: “How many tables have been taken in the observed period?” (none, few, less than half, appr. half, more than half, almost all, all)
Concomitant medication	No, yes => please specify

Arthralgia – Module (to be filled in in case of arthralgia occurrence during anastrozole therapy)	

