Subjective perception of side-effects will be evaluated using the following scores: GASE-P (Generic Assessment of Side Effects, appendices E and F), SASS (Somatosensory Amplification Scale, appendices E and F), and BMQ (Beliefs about medicines questionnaire, appendices E and F).

Arthralgia therapy and related costs

Arthralgia therapy will be documented in the eCRF and in the patient questionnaire (for further information, see Chapter 8; e.g., newly prescribed medication, doctor’s visits, diagnostics, hospital admissions). Diagnostic and therapeutic measures will be recorded as standardised patterns in the eCRF and in the patient questionnaire and will be correlated with itemised costs for evaluation purposes. Cost evaluations will be feasible on patient and global level.

Each occurrence of arthralgia will be assigned to the corresponding time interval according to 0-3, 3-6, 6-9, 9-12 and 12+ months after the start of anastrozole treatment (i.e. post treatment start).

Validation of data (arthralgia therapy and compliance) by sick fund data

For patients who signed an additional informed consent form (Appendix C, see chapter 7.3), arthralgia therapy as documented by the investigators and the patients will be compared to sick fund data on an individual patient level by a third party who will combine the study and the sick fund datasets on an individual patient level. The third party will combine the sick fund dataset and the study dataset using the patient insurance number which will be sent to on the additional informed consent (Appendix C). The patient insurance number will be immediately deleted after data combination. Statistical evaluation will only be based on pseudonymised data.

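### Arthralgia incidence, time to first arthralgia and the score comparison ignore arthralgia present before anastrozole, so the upfront/switch contrast can mix earlier and new joint pain

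*Protocol*

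**What the plan says.** The Protocol fixes three arthralgia analyses in section 11.4.1:

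- **Incidence.** The objective is "Incidence of arthralgias and arthralgia characteristics within the first year of anastrozole therapy¹ stratified by upfront and switch therapy", and the measure is the number and percentage of "patients with at least one event of arthralgia within pre-defined intervals". Section 11.2 supplies the allocation rule: "Each occurrence of arthralgia will be assigned to the corresponding time interval", counted from the start of anastrozole.
- **Time to event.** Time from the start of anastrozole to first arthralgia, by Kaplan-Meier.
- **Score.** The mean of the 14 VAS items, compared between groups by t-test.

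Arthralgia before anastrozole is collected twice. The doctor's baseline form in section 8.1.2 asks for "pre-existing arthralgias before anastrozole therapy? => if yes: intensity? localisation? duration", and the patient's start questionnaire in section 8.2.1 also asks about it. The analysis stated for this status is: "The absolute and percentage number of patients with pre-existing arthralgias will be calculated stratified by upfront and switch therapy".

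The upfront/switch contrast is an aim. Section 1.3 says the study "assesses whether the incidence and severity of arthralgias is different in upfront anastrozole therapy" compared with anastrozole after two to three years of tamoxifen. The Synopsis states that there is no randomisation.

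**The concern.** No at-risk condition is attached to incidence or to time to first arthralgia, and the score comparison does not use prior status. Switch patients arrive after two to three years of another endocrine drug and upfront patients do not, so equal prior joint pain cannot be taken for granted.

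If the two groups differ in prior arthralgia, and women with a history are more likely to have an episode on treatment, the crude figures will differ even where anastrozole causes new arthralgia equally often in both. A reader would then take a difference in history for a difference between the two treatment sequences. The VAS score is open to the same problem. Women enter after three to six months of anastrozole (section 6), so there is no pre-treatment score to subtract.

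**Working it through.** **Can women with earlier arthralgia enter the numerator?**

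- The eligibility criteria (6.1) do not exclude them.
- Neither analysis set (11.3) removes them.
- On the baseline form (8.1.2), prior arthralgia and arthralgia after the start of anastrozole are separate items. A yes to the second opens the arthralgia module, whatever the answer to the first.
- The module (8.1.2, 8.1.3) asks about onset during anastrozole therapy. Unchanged old pain may therefore go unrecorded by the doctor, but a new or worse episode in such a woman is recorded and counts.

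**Figures in the plan.** The Protocol gives no figure for incidence or for prior arthralgia, so there is none to reproduce on this point. Its sample sizes reproduce (1119 per group for 44% versus 50% with continuity correction; 393.4, so 394, per group for a difference of 0.4 with SD 2) and are not in question.

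**Size of the possible artefact.** Let p be the prevalence of pre-existing arthralgia, c the chance that a woman with it has a recorded event on treatment (recurrence), and r the new-onset risk, set equal in both groups.

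- Crude incidence = p·c + (1 − p)·r
- Spurious gap = (p_switch − p_upfront) × (c − r)

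All inputs are assumptions. The value 29.4% is the tamoxifen joint-disorder figure in section 1.1, used only as a scenario for prevalence in switch patients.

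| Pre-existing, upfront vs switch | c | r | Gap |
|---|---|---|---|
| equal | any | any | 0 |
| any | equal to r | equal to c | 0 |
| 20% vs 25% | 60% | 30% | 0.05 × 0.30 = 1.5 points |
| 20% vs 25% | 100% | 20% | 0.05 × 0.80 = 4.0 points |
| 20% vs 29.4% | 60% | 30% | 0.094 × 0.30 = 2.8 points |
| 20% vs 29.4% | 80% | 20% | 0.094 × 0.60 = 5.6 points |
| 20% vs 29.4% | 100% | 20% | 0.094 × 0.80 = 7.5 points |

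The 5.6-point case in full:

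- Upfront: 0.20 × 0.80 + 0.80 × 0.20 = 32.0%
- Switch: 0.294 × 0.80 + 0.706 × 0.20 = 37.6%

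If prevalence were higher in upfront patients, the sign would reverse. At equal prevalence of 20% the contrast is clean, but the crude figure is 32% where new-onset risk is 20%.

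**Would such a gap be noticed?** Assume 3212 × 0.7 / 2 = 1124 evaluable women per group; the equal split is an assumption. A two-sided 5% comparison reaches significance with probability Φ((gap − 1.96·SE₀)/SE₁), where SE₀ is the pooled and SE₁ the unpooled standard error. For 20% versus 29.4% this runs from 28% (gap 2.8) to 95% (gap 7.5), with 80% at 5.6 points. For 20% versus 25% it runs from 11% to 50%.

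**Score.** If women with prior arthralgia score d points higher on average, the spurious mean difference is (difference in prevalence) × d. The documents give no d. Taking d as one SD, 2 points (11.5), gives 0.05 × 2 = 0.10 to 0.094 × 2 = 0.19, against the difference of 0.4 used for sample size.

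**The case against.** The strongest case on the other side has five parts.

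1. **Old pain may not be an event.** The doctor's module asks about onset during therapy, and section 11.4.2 leaves adverse events with onset before the start date out of the analysis. This stands in part. It lowers c and shrinks the gap. But the 11.4.2 rule is written for the adverse-event analysis, and section 8.3.1.1 counts deterioration of an existing condition as an adverse event, so new or worse episodes remain. The patient's follow-up item does not separate old from new pain, but section 11.3 ties the determination of incidence to CRF documentation, so the point does not rest on that item.
2. **The comparison is mild.** No test is named for incidence, all p-values are exploratory (11.1), and prior arthralgia is tabulated in the same strata, so an imbalance would be visible. This stands as a limit on the harm. A visible imbalance still does not show how much of a difference it explains.
3. **Prior status may be used elsewhere.** The risk-factor objective refers to treatment-emergent arthralgia, which would need prior status or an onset date. The term is not defined and is not applied to incidence or to time to first arthralgia.
4. **This is detail for the statistical analysis plan.** Section 11.4 does leave details there. But the incidence measure and the t-test are named in the Protocol itself.
5. **Restriction has its own bias.** Joint pain in a switch patient may have arisen on tamoxifen and so belong to the sequence being compared. Total burden is also what the compliance and cost objectives need. This stands, and it is why the overall figures should be kept.

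**Conclusion.** The point holds in a limited form. Section 11.4.1 sets crude measures for a non-randomised contrast that section 1.3 makes an aim, and leaves unused a relevant pre-treatment variable that is already collected. As written, the analyses cannot separate a difference in new arthralgia from a difference in history.

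The size is unknown. It is zero at equal prevalence or equal risks, and about 1.5 to 7.5 points over the assumed ranges (20% versus 25–29.4% pre-existing, 60–100% recurrence, 20–30% new onset). For the score it is roughly 0.1 to 0.2 points if a history adds one SD.

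A reader might infer three stronger things that the documents do not support:

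- **That every woman with earlier joint pain is automatically counted as a case.** The Protocol does not say so. Their inclusion follows from the absence of a restriction and from the form routing, and unchanged pain may not be recorded.
- **That an upfront/switch difference would be an artefact.** No prevalence is given, so neither the size nor the direction can be predicted.
- **That women free of earlier arthralgia must become the main population.** That is debatable, because pain on tamoxifen may be part of the switch sequence.

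**What to change.** In Protocol section 11.4.1, and carried into the statistical analysis plan:

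- Keep overall interval incidence and the overall Kaplan-Meier curve.
- Add both, split by pre-existing arthralgia within upfront and within switch: new onset in women without it, new or worsened arthralgia in women with it.
- Base any statement about a difference in new-onset arthralgia on the women without it.
- Report beside the t-test a linear model for the mean VAS score with therapy group and pre-existing arthralgia (yes/no).
- State whether the doctor's or the patient's record defines pre-existing status.

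The cost is some wording, one more table split and one extra model. No new data are needed. The downside is that prior arthralgia is recalled and, in switch patients, may partly reflect tamoxifen. Unadjusted and adjusted results should therefore be shown together, neither replacing the other.
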